4.6.2. Time and Events Table Part B

Procedures	Screening	Optional Baseline Run In Visit ¹	Day 1	Day 4	Day 7	Day 14	Day 15	Follow-up	
Visit Window (relative to Day 1)	-28 to -14 days		Exams/samples pre-dose					7-10 days post last dose	
Clinic Visit	X	X	X	X	X	X	X	X	X
Informed Consent	X								
Demographics	X								
Complete physical	X								
Brief physical		X	X	X	X	X	X	X	X
Medical/medication/drug/alcohol history	X	X							
12-lead ECG ²	X		X				X		
Vital signs ³	X		X		X		X	X	X
Urine pregnancy(females)	X		X					X	
Hema/Chem/ Safety Labs ⁴	X		X		X		X	X	
Vascular Perfusion Eligibility Assessments ⁵	X								
Blood samples for HIF α , (e.g., EPO, Hepcidin, VEGF) ⁶			X		X		X		
Standard of Care Treatment ⁷	X	X	<=====>					X	X
Study Treatment/Dosing In the Clinic ⁸			X	X	X	X			

Procedures	Screening	Optional Baseline Run In Visit ¹	Day 1	Day 4	Day 7	Day 14	Day 15	Follow-up	
PK serial blood sampling ⁹			X		X	X	X		
PK Trough Sample ⁹									
Tissue Biopsies (gene expression, macrophage and bioburden analysis) ¹⁰			X		X		X		
Wound Fluid (cytokine and bioburden analysis) ¹¹			X		X		X	X	
SensiLase (Doppler blood flow)			X		X		X	X	
Physical Characteristics (assessed pre-dose) ¹²	X	X	X	X	X		X	X	
Clinical Characteristics ¹³	X		X	X	X	X	X	X	
Concomitant Medication Review			X	<=====>				X	X
Adverse Event Assessment ¹⁴			X	<=====>				X	X

1. Optional Baseline Run In visit: This optional visit is for subjects that will exceed the 14 (± 1 day) Run-in window between screening and Day 1.
2. Single ECGs will be taken at Screening and pre-dose on Day 1 and 24h post-last dose on Day15. ECGs should be taken while subject is supine for at least 5 minutes. Additional ECGs may be taken at the discretion of the investigator as needed based on symptoms or ECG findings.

3. Assessment of vital signs (including blood pressure and heart rate) will be performed at Screening and pre-dose on Days 1, 7, 15 (24h post-last dose), and at Follow-up Visits. Vital signs should be performed after resting in a supine or semi-supine position for at least 5 minutes.
4. Blood samples for safety will be collected fasting at Screening and pre-dose/equivalent time on Days 1, 7, 15 (24h post-last-dose), and at the 7-10 day Follow-up Visit. Refer to Section 7.2.4 for specific laboratory parameters to be tested.
5. See Item 7 in the Inclusion Criteria – DFU Subjects for acceptable perfusion parameters. Only 1 test of the 4 (TcPO₂, ABI, toe pressure, Doppler ultrasound) is required for eligibility.
6. Blood samples for HIF α activation will be collected at pre-dose/equivalent time.
7. All subjects will be on SOC throughout the study (Section 7.4).
8. In between clinic visits, subjects will perform applications of study drug at home.
9. See separate Time and Events table for serial PK sampling details for Days 1, 7 and 14 and the associated 24 time point. Refer to Section 7.12 for details on the collection and processing of PK samples. PK sampling times may be changed based on the observed GSK1278863 PK profile.
10. Direct wound tissue biopsies will be collected at pre-dose/equivalent on Days 1, 7, and 15, however based on emerging data, time points may be added or deleted; wounds that have healed sufficiently may be exempt. Refer to Section 7.7.2 for additional details on the collection and processing of tissue biopsies.
11. Wound fluid will be collected at pre-dose/equivalent on Days 1, 7, 15 and at the 7-10 day Follow-up Visit. Refer to the Section 7.7.1 for additional details on the collection and processing of wound fluid samples.
12. Physical characteristics of the wound (i.e., photos of the wound and wound measurement assessments) will be assessed at Screening (Optional Baseline Run In Visit), at pre-dose/equivalent time on Days 1, 4, 7, 15 and at the 7-10 day Follow-up Visit.
13. Clinical characteristic assessments of the DFU begin with Section 7.10 and contain instructions for completing the assessments including the irritation/symptom scale as needed. Assessments are recorded in the eCRF.
14. Adverse events are to be collected from first dose through the final Follow-up visit.

4.6.3. Serial PK Time and Events Table Part B

VIST DAY	Part B Serial PK Sampling ^{1,2}								
	Pre-dose	Hours (h)							
		1h	2h	4h	8h	10h	11h	12h	24h
Day 1	X		X						
Day 7	X		X						
Day 14 OUT-PATIENTS	X	X	X	X	X	X ³			X
Day 14 IN-PATIENTS	X	X	X	X	X			X	X

1. Patients are permitted to either stay in clinic (in-patients) or be discharged and return for clinic visits (out-patients). Refer to Section 7.12 for details on the collection and processing of PK samples.
2. PK sampling times may be changed based on observed GSK1278863 PK profile.
3. Sample must be taken within the 10 to 12 hour time window.

5. STUDY POPULATION

5.1. Number of Subjects

Enough subjects will be enrolled in Part A (Single Doses) such that approximately 32 subjects (~8 healthy volunteers in Cohort 1, and ~24 DFU subjects in Cohorts 2, 3 and 4) complete dosing and critical assessments. If optional cohort(s) are utilized, each cohort will enroll approximately 8 subjects (6 on active drug, 2 on placebo).

In Part B, enough subjects will be enrolled such that approximately 48 subjects in Part B (~16 DFU subjects per cohort) complete dosing and critical assessments (assumes approximately 3 cohorts).

Additional subjects/cohorts may be enrolled to allow for evaluation of additional dose levels, based on emerging data. The IRB will be informed if any additional cohorts (including optional cohorts) are included in the study based on local site requirements.

If subjects prematurely discontinue the study, additional subjects may be enrolled as replacement subjects and assigned to the same treatment sequence at the discretion of the GSK Medical Monitor in consultation with the Investigator.

5.2. Eligibility Criteria – Healthy Volunteers (Part A Cohort 1)

5.2.1. Inclusion Criteria - Healthy Volunteers (Part A Cohort 1)

Specific information regarding warnings, precautions, contraindications, adverse events, and other pertinent information on the GSK investigational product or other study treatment that may impact subject eligibility is provided in the IB [GlaxoSmithKline Document Number [RM2008/00267/07](#)] Deviations from inclusion criteria are not allowed because they can potentially jeopardize the scientific integrity of the study, regulatory acceptability or subject safety. Therefore, adherence to the criteria as specified in the protocol is required.

A subject will be eligible for inclusion in this study only if all of the following criteria apply:

1. ALT, alkaline phosphatase and bilirubin $\leq 1.5 \times \text{ULN}$ (isolated bilirubin $> 1.5 \times \text{ULN}$ is acceptable if bilirubin is fractionated and direct bilirubin $< 35\%$).
2. Single QTc $< 450 \text{ msec}$.
3. Healthy as determined by a responsible and experienced physician, based on a medical evaluation including medical history, physical examination, laboratory tests and ECGs. A subject with a clinical abnormality or laboratory parameters outside the reference range for the population being studied may be included only if the Investigator and the GSK Medical Monitor agree that the finding is unlikely to introduce additional risk factors and will not interfere with the study procedures. Subjects with Hb values higher than ULN the normal range should always be excluded from enrollment.

4. Male or female between 18 and 90 years of age inclusive, at the time of signing the informed consent.
5. A female subject is eligible to participate if she is of:
 1. Childbearing potential, and agrees to use one of the approved contraception methods as outlined in Section 8.1 from Screening until completion of the Follow-up Visit OR
 2. Non-childbearing potential (NCBP) defined as pre-menopausal females with a documented tubal ligation or hysterectomy; or postmenopausal defined as 12 months of spontaneous amenorrhea [in questionable cases a blood sample with simultaneous follicle stimulating hormone (FSH) > 40MIU/ml and estradiol < 40pg/mL (<147pmol/L) is confirmatory]. Females on hormone replacement therapy (HRT) and whose menopausal status is in doubt will be required to use one of the contraception methods in Section 8.1 if they wish to continue their HRT during the study. Otherwise, they must discontinue HRT to allow confirmation of post-menopausal status prior to study enrollment. For most forms of HRT, at least 2-4 weeks should elapse between the cessation of therapy and the blood draw; this interval depends on the type and dosage of HRT (consult with GSK Medical Monitor). Following confirmation of their post-menopausal status, they can resume use of HRT during the study without use of a contraceptive method.

5.2.2. Exclusion Criteria – Healthy Volunteers (Part A Cohort 1)

Deviations from exclusion criteria are not allowed because they can potentially jeopardize the scientific integrity of the study, regulatory acceptability or subject safety. Therefore, adherence to the criteria as specified in the protocol is required.

A subject will not be eligible for inclusion in this study if any of the following criteria apply:

1. A positive pre-study Hepatitis B surface antigen or positive Hepatitis C antibody result within 3 months of screening
2. Current or chronic history of liver disease, or known hepatic or biliary abnormalities (with the exception of Gilbert's syndrome or asymptomatic gallstones).
3. History of malignancy within 5 years of Screening or those with a strong family history of cancer (e.g., familial cancer disorders), with the exception of squamous cell or basal cell carcinoma of the skin that has been definitively treated.
4. A history of drug or alcohol abuse, or a history of regular alcohol consumption within 6 months of the study defined as an average weekly intake of >14 drinks for males or >7 drinks for females. One drink is equivalent to 12g of alcohol: 12 ounces (360mL) of beer, 5 ounces (150mL) of wine or 1.5 ounces (45mL) of 80 proof distilled spirits.
5. A positive test for HIV antibody.

6. The subject has participated in a clinical trial and has received an investigational product within the following time period prior to the first dosing day in the current study: 30 days, 5 half-lives (whichever is longer).
7. Unable to refrain from the use of prescription or non-prescription drugs, including vitamins, herbal and dietary supplements (including St John's Wort) within 7 days (or 14 days if the drug is a potential enzyme inducer) or 5 half-lives (whichever is longer) prior to the first dose of study medication, unless in the opinion of the Investigator and GSK Medical Monitor the medication will not interfere with the study procedures or compromise subject safety.
8. History of sensitivity to any of the study medications, or components thereof or a history of drug or other allergy that, in the opinion of the investigator or GSK Medical Monitor, contraindicates their participation.
9. Where participation in the study would result in donation of blood or blood products in excess of 500mL within a 56 day period
10. Pregnant females as determined by positive urine hCG test at screening or prior to dosing.
11. Unwillingness or inability to follow the procedures outlined in the protocol.
12. Subject is mentally or legally incapacitated.

5.3. Eligibility Criteria – DFU Subjects

5.3.1. Inclusion Criteria – DFU Subjects

Deviations from inclusion criteria are not allowed because they can potentially jeopardize the scientific integrity of the study, regulatory acceptability or subject safety. Therefore, adherence to the criteria as specified in the protocol is required.

A DFU subject will be eligible for inclusion in this study only if all of the criteria listed are met.

1. Diagnosed with Type I or Type II diabetes mellitus.
2. HbA1c \leq 12%.
3. Single QTc \leq 500msec, or \leq 530msec in subjects with bundle branch block. No QTc exclusion for subjects with a predominantly paced rhythm.
4. Lower extremity diabetic foot ulcer of 30-364 days' duration.
5. DFU between 1cm² and 22cm² at screening.
6. Presence of at least one DFU that meets all of the following criteria:
 - a. Ulcer has been diagnosed as a full-thickness, neuropathic DFU and is located at or distal to the malleolus (excluding ulcers between the toes but including those of the heel).

- b. There is a minimum 2cm margin between the qualifying study ulcer and any other ulcers on the specified foot.
- c. Ulcer size (area) $\geq 1\text{cm}^2$ and $\leq 16\text{cm}^2$ (post-debridement at time of randomization).
- d. Wagner Grade 1.
- e. Depth $\leq 5\text{mm}$ with no capsule, tendon or bone exposed and no tunneling, undermining, or sinus tracts.

Note: If the subject has more than one qualifying DFU, the ulcer designated as the study ulcer will be at the discretion of the Investigator. Non-study ulcers being treated during the course of the study will be treated with moist wound therapy Standard of Care (SoC) identified under this study).

- 7. Adequate vascular perfusion of the affected limb within 30 days of screening, as defined by at least one of the following:
 - a) $\text{TcPO}_2 > 35\text{mmHg}$.
 - b) Ankle-Brachial Index (ABI) ≥ 0.6 and ≤ 1.2
 - c) Toe pressure (plethysmography) $> 50\text{mmHg}$.
 - d) Doppler ultrasound (biphasic or triphasic waveforms) consistent with adequate blood flow to the affected extremity, as determined by SoC.
- 8. ALT, alkaline phosphatase and bilirubin $\leq 1.5 \times \text{ULN}$ (isolated bilirubin $> 1.5 \times \text{ULN}$ is acceptable if bilirubin is fractionated and direct bilirubin $< 35\%$).
- 9. Male or female between 18 and 90 years of age inclusive, at the time of signing the informed consent.
- 10. A female subject is eligible to participate if she is of:
 1. Childbearing potential, and agrees to use one of the approved contraception methods as outlined in Section 8.1 from Screening until completion of the Follow-up Visit OR,
 2. Non-childbearing potential (NCBP) defined as pre-menopausal females with a documented tubal ligation or hysterectomy; or postmenopausal defined as 12 months of spontaneous amenorrhea [in questionable cases a blood sample with simultaneous follicle stimulating hormone (FSH) $> 40\text{MIU/ml}$ and estradiol $< 40\text{pg/mL}$ ($< 147\text{pmol/L}$) is confirmatory]. Females on hormone replacement therapy (HRT) and whose menopausal status is in doubt will be required to use one of the contraception methods in Section 8.1 if they wish to continue their HRT during the study. Otherwise, they must discontinue HRT to allow confirmation of post-menopausal status prior to study enrollment. For most forms of HRT, at least 2-4 weeks should elapse between the cessation of therapy and the blood draw; this interval depends on the type and dosage of HRT (consult with GSK Medical Monitor). Following confirmation of their post-menopausal status, they can resume use of HRT during the study without use of a contraceptive method.

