4.5.1.3. QTc Withdrawal Criteria

Healthy Volunteers (Part A, Cohort 1)

A subject that meets criteria below will be withdrawn from the study. The QT correction formula used to determine discontinuation should be the same one used throughout the study.

- QTc $>$ 500msec

Withdrawal decisions are to be based on an average QTc value of triplicate ECGs. If an ECG demonstrates a prolonged QT interval, obtain 2 more ECGs over a brief period, and then use the averaged QTc values of the 3 ECGs to determine whether the subject should be discontinued from the study.

DFU Patients (Part A Cohorts 2 through Final Cohort, Part B All Cohorts)

A subject who meets the criteria below will be withdrawn from the study. The QT correction formula used to determine discontinuation should be the same one used throughout the study.

- QTc $>$ 530msec or uncorrected QT $>$ 600msec
- If subject has underlying bundle branch block then the QTc withdrawal criteria depends on the baseline value:

Baseline QTc value with underlying bundle branch block)	QTc withdrawal criteria
≤500msec	>530msec
≤530 msec	≥550msec

Withdrawal decisions are to be based on an average QTc value of triplicate ECGs. If an ECG demonstrates a prolonged QT interval, obtain 2 more ECGs over a brief period, and then use the averaged QTc values of the 3 ECGs to determine whether the subject should be discontinued from the study.

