7.2.3. Electrocardiogram (ECG)

Single 12-lead ECGs will be obtained at each timepoint during the study using an ECG machine that automatically calculates the heart rate and measures PR, QRS, QT, and QTc intervals. The subject will be resting in a supine position for at least 5 minutes prior to the procedure. Refer to Section 4.5.1.3 for QTc withdrawal criteria and additional QTc readings that may be necessary.

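### Paced DFU subjects may enter at any QTc but fall under an absolute QTc withdrawal limit, and the bundle-branch-block withdrawal bands overlap each other and conflict with the general limit

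*Protocol*

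**What the plan says.** **Entry.** Protocol Section 5.3.1, criterion 3, accepts a single QTc of at most 500 msec, or at most "530msec in subjects with bundle branch block", and then states: "No QTc exclusion for subjects with a predominantly paced rhythm".

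**Withdrawal.** Section 4.5.1.3 has a block headed "DFU Patients (Part A Cohorts 2 through Final Cohort, Part B All Cohorts"). It is mandatory: "A subject who meets the criteria below will be withdrawn from the study". The general limit is a QTc above "530msec or uncorrected QT" above 600 msec. A second bullet adds: "If subject has underlying bundle branch block then the QTc withdrawal criteria depends on the baseline value". Its table has two rows:

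- baseline at most 500 msec: withdraw above 530 msec
- baseline at most 530 msec: withdraw at 550 msec or more

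**Confirmation.** "Withdrawal decisions are to be based on an average QTc value of triplicate ECGs", so two further ECGs follow a prolonged one before any decision.

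**Elsewhere.** Section 7.2.3 adds no rule of its own: "Refer to Section 4.5.1.3 for QTc withdrawal criteria and additional QTc readings that may be necessary". Section 4.1 rules out waivers and exemptions other than for immediate safety concerns.

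**The concern.** Entry and withdrawal rules should fit together, so that a subject properly admitted does not meet a stopping criterion by virtue of the baseline condition alone. Here one group, subjects with a predominantly paced rhythm, has no upper limit at entry and an absolute limit afterwards. A second group, subjects with BBB, is given rows and a general limit that can call for opposite actions on the same averaged ECG.

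Three things are at stake:

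- subjects whom the protocol deliberately admits could be lost before dosing;
- withdrawals after dosing could reflect pacing or conduction delay and not the ointment;
- two sites could decide differently on identical readings.

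ECGs belong to the primary safety endpoint (Section 3.1), so the rule bears on data the study is meant to describe.

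**Working it through.** There is no plan figure to reproduce. The check applies the two sections literally, side by side.

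**1. Entry limit against the general QTc withdrawal limit (above 530 msec)**

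| Group | Entry limit (5.3.1) | Eligible baselines already above 530 |
|---|---|---|
| Not paced, no BBB | at most 500 | none (500 is below 530) |
| Not paced, BBB | at most 530 | none (530 is not above 530) |
| Paced, with or without BBB | none | every baseline above 530 |

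On QTc, the contradiction at entry comes only from the paced clause. A paced subject with BBB and a baseline above 530 also falls in neither row of the BBB table, which leaves only the general limit.

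**2. The BBB table read row by row**

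The second row gives an upper bound for baseline and no lower bound. Any baseline of at most 500 is also at most 530, so both rows apply to it.

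| Baseline | Averaged on-study QTc | Row 1 (above 530) | Row 2 (550 or more) | General limit (above 530) |
|---|---|---|---|---|
| 480 | 530 | stay | stay | stay |
| 480 | 540 | withdraw | stay | withdraw |
| 480 | 550 | withdraw | withdraw | withdraw |
| 520 | 530 | row does not apply | stay | stay |
| 520 | 540 | row does not apply | stay | withdraw |
| 520 | 550 | row does not apply | withdraw | withdraw |

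For baselines of at most 500, the rows disagree when the averaged QTc is above 530 and below 550. In whole milliseconds that is 531 to 549, or 549 − 531 + 1 = 19 values. For baselines of 501 to 530, only row 2 applies, but it disagrees with the general limit over the same 19 values unless the table is read as replacing that limit. The text does not say that it does.

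**3. Whether anything else resolves it**

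Section 7.2.3 points back to 4.5.1.3. Triplicate averaging reduces measurement noise, but it neither exempts a stable paced QTc nor chooses between rows. Section 4.1 leaves a site no general power to exempt a subject.

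**4. Where a withdrawal would appear**

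- *Scheduled ECGs, Part A (4.6.1):* Screening, Day 1 pre-dose, Day 3 (48 h), and the 7-10 day follow-up.
- *Scheduled ECGs, Part B (4.6.2):* Screening, Day 1 pre-dose, and Day 15, 24 h after the last of 14 daily applications. Unscheduled ECGs are allowed in both parts.
- *Tables:* SAP Section 5 limits the All Subject Population to subjects with at least one dose. SAP Sections 14.1.1 and 14.1.2 use that population for disposition, AE and ECG tables. Protocol Section 5.4 keeps screen and baseline failure data at the site.

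A subject withdrawn before dosing is therefore outside those tables. A subject withdrawn after dosing is inside them.

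**5. Scale of a single post-dose withdrawal**

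Target arm sizes come from Protocol Section 6.2.1 and SAP Section 3.1. One withdrawal is 1/6 = 17% of a Part A active arm, 1/12 = 8% of the Part B active arm, and 1/2 = 50% of a placebo or standard-of-care arm within a cohort. These figures show what one case would weigh; they do not estimate how many there will be.

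**The case against.** The best reply is that the practical effect is small, and much of it stands.

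- **Reporting.** A reader might infer that withdrawals at baseline would distort the disposition and safety tables. The documents do not support that: those tables require at least one dose.
- **Trigger.** A reader might also infer that a single prolonged ECG removes a subject. It does not, because the average of three decides.
- **Part B exposure.** The only scheduled post-dose ECG comes after all 14 applications, and withdrawn subjects are still asked to complete follow-up (4.2.2.4). A withdrawal on a scheduled ECG would not shorten dosing once it had begun.
- **Part A.** A Day 3 withdrawal could cost a second dosing period. However, the paced clause arrived with Amendment 7, whose rationale already cites results at 1% ointment and 100 mg/cm². The SAP lists that strength and amount for its last Part A regimen (E) and for the Part B regimen. This suggests that most Part A enrolment came before the clause. The SAP also limits Part B to one cohort, with a target of 16.
- **BBB rows.** If row 2 covered every baseline up to 530, row 1 would be pointless if row 2 prevailed. An omitted lower bound is the likely explanation, and the bands before Amendment 7 did not overlap.

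Two things do not fall away. An intended lower bound that is not written cannot be applied uniformly, and supplying it would still leave the general limit in conflict with row 2. Nothing in either document reconciles the paced clause with the withdrawal limit, although the Amendment 7 rationale says the withdrawal criteria were modified to align with the new eligibility criteria.

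**Conclusion.** This is an internal inconsistency between Sections 5.3.1 and 4.5.1.3, and it is wrong as written. A paced subject with a stable QTc above 530 msec, or an uncorrected QT above 600 msec, is eligible and already meets withdrawal. A BBB subject with a baseline up to 500 has two conflicting rows when the averaged QTc is above 530 and below 550. One with a baseline of 501 to 530 has row 2 in conflict with the general limit over the same range.

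The size is limited. The documents do not say how many subjects are paced or have BBB, and the number affected may be zero. The effects to expect are loss of eligible subjects before dosing; occasional withdrawals after dosing unrelated to treatment (Part A Day 3 or 7-10 day follow-up, Part B Day 15, or an unscheduled ECG); and inconsistent site decisions. Replacement is allowed (5.1), so cohort size can be restored, but a post-dose withdrawal would still be reported. With no formal hypothesis (6.1), a stronger claim that a treatment comparison would be biased is not supported.

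The conclusion rests on reading the text literally and on two assumptions: that the withdrawal rule applies from entry, and that the paced subject's QTc is stable. If the rule were meant to start only after dosing, the paced conflict would appear at the first post-dose ECG instead of at baseline.

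**What to change.** Amend Section 4.5.1.3 and cross-refer it to criterion 3 of Section 5.3.1, so that the text states:

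1. whether, and how, the QTc and QT withdrawal rule applies to subjects with a predominantly paced rhythm, including those with BBB whose baseline lies above both table rows;
2. BBB baseline bands that are mutually exclusive, each with a lower and an upper bound;
3. whether the BBB table replaces the general limit for subjects with BBB or applies alongside it.

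The sponsor's medical team chooses all thresholds, and none is proposed here. The cost is protocol wording and a matching site instruction. No analysis, sample size or data collection changes. If enrolment is already complete, the study report should state how the rule was applied to any paced or BBB subject and identify any withdrawal made under it.
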